8.4.3 Safety Analyses

Summary tables will be presented on safety parameters for each treatment arm. Toxicity rates (worst CTC grade per subject) of adverse events and laboratory tests, both of any occurrence and severe (Grade ≥ 3) will be tabulated. Shift tables for selected laboratory parameters will be produced.

[REDACTED]

8.4.7 Outcomes Research Analyses

8.4.7.1 Analysis of HRQoL Data

All analyses will be conducted on randomized subjects. Questionnaire completion rate, defined as the proportion of questionnaires actually received out of the expected number (ie, the number of subjects still on treatment), will be calculated and summarized at each assessment point. Subjects without any post-baseline assessment will be excluded from the analysis.

The comparison between the 2 treatment arms of the change from baseline in the mean score of pain severity will be conducted using a longitudinal mixed model with treatment arm, time point (categorical), and baseline score as fixed effects and a banded covariance matrix (constant covariances on each diagonal of the matrix). Similar model will be used to analyze change from baseline in mean score of pain interference.

Adjusted mean change from baseline at each assessment point will be graphically presented by randomized arm for the three questionnaires [REDACTED] and BPI-SF).

[REDACTED]

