The key secondary endpoints are:

- Objective response rate
- Overall survival

Objective response rate (ORR) is defined as the proportion of randomized subjects who have a best overall response of partial response or better. Overall survival is the time from randomization until death. Subjects who do not die will be censored at the date of last contact.

A hierarchical procedure will be used to ensure a two sided family-wise type I error rate of 5% for testing the one primary and two key secondary endpoints. If there is a statistically significant improvement in PFS, then ORR will be compared between arms at the two-sided 5% level. If the comparison of ORR is also statistically significant, then survival will be compared between arms using a two-sided 5% level sequential test procedure.

Objective response rate will be compared between randomized arms using a two-sided 5% level Cochran-Mantel Haenszel (CMH) test stratified by the same factors used in the analysis of PFS. An associated odds ratio and 95% confidence interval will be calculated. The response rate and its corresponding 95% confidence interval will also be calculated for each treatment arm. There will be no interim comparison of this endpoint.

Survival will be compared between treatment arms using two-sided, stratified log-rank tests at the interim and final looks. The family-wise type I error rate for the sequential testing procedure will be 5% and the stratification factors will be the same as those used for the randomization. The significance level at the interim and final analyses of survival will be determined using an O'Brien and Fleming α spending function.

Other Secondary endpoints include change from baseline in mean score of pain severity and mean score of pain interference using the BPI-SF. The two endpoints will be tested at the 2-sided 2.5% level each and will not be part of the hierarchical testing procedure. For these two endpoints, comparison will be conducted using a longitudinal mixed model with treatment arm and time point (categorical) and baseline score as fixed effects and a banded covariance matrix (covariances are constant on each diagonal of the matrix).

TABLE OF CONTENTS

TITLE PAGE 1

DOCUMENT HISTORY 3

SYNOPSIS 5

TABLE OF CONTENTS 9

1 INTRODUCTION AND STUDY RATIONALE 13

[REDACTED] [REDACTED]

1.2 Research Hypothesis 14

1.3 Objectives 15

 1.3.1 Primary Objective 15

 1.3.2 Secondary Objectives 15

[REDACTED] [REDACTED]

2 ETHICAL CONSIDERATIONS 34

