4.2 Method of Assigning Subject Identification

After the subject's eligibility is established and informed consent has been obtained, the subject must be enrolled into the study by calling an interactive voice response system (IVRS) to obtain the subject number. The following information is required for subject enrollment:

- Date of Birth
- Site number
- Date that informed consent was obtained

Instructions on the use of interactive voice response system will be provided at site initiation.

When it has been determined that a subject is eligible for randomization, a call will be placed to IVRS to obtain treatment assignment. Subjects will be randomized to lenalidomide/dexamethasone + elotuzumab (Arm A) or lenalidomide/dexamethasone alone (Arm B) in a 1:1 ratio. The randomization will be stratified by the following factors:

- Stage of Disease (International Staging System 1 - 2 versus 3)
- Age (< 75 years old versus ≥ 75 years old)
- ECOG Performance Status (0 versus 1 - 2)

and will be carried out via permuted blocks within each stratum.

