8.4.2.3 Secondary Efficacy Analyses

The key secondary endpoints are:

- Objective response rate (ORR)
- Overall survival

A hierarchical procedure will be used to ensure a two-sided, family-wise type I error rate of 5% for testing the one primary and two key secondary endpoints. If there is a statistically significant improvement in PFS, ORR will be compared between arms at the 5% level. If the comparison of ORR is also statistically significant at the 5% level, then survival will be compared between arms using a 5% level sequential test procedure.

Objective response will be compared between randomized arms using a two-sided 5% level Cochran-Mantel Haenszel (CMH) test stratified by the same factors used in the analysis of PFS. An associated odds ratio and 95% confidence interval will be calculated. The response rate and its corresponding 95% confidence interval will also be calculated for each treatment arm. There will be no interim comparison of this endpoint.

Survival will be compared between treatment arms using two-sided, stratified log-rank tests at the interim and final looks. The family-wise type I error rate for the sequential testing procedure will be 5% and the stratification factors will be the same as those used for the randomization. The significance level at the interim and final analyses of survival will be determined using an O'Brien and Fleming α spending function.

Other Secondary objectives are:

- Change from baseline of mean score of pain severity and change from baseline of mean score of pain interference (BPI-SF)

Each of the two comparisons will be made at the two-sided type I error of 2.5% and will be tested independent of the significance of the comparison of the progression-free survival, objective response rate and overall survival. See [Section 8.4.7.1](#) for details about analyses.

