6 STUDY PERIODS, TREATMENT REGIMENS AND POPULATIONS FOR ANALYSES

6.1 Study Periods

There are three periods in this study: screening, on-treatment and post-treatment follow-up.

Screening: Most screening procedures must be done no more than 14 days prior to randomization. Some exceptions include efficacy assessments and ECGs, which can be done up to 28 days prior to randomization. See Section 5 of the Protocol for full details of study procedures and timings. For analyses purposes data collected within 60 days of randomization and prior to first dose will fall into the screening/baseline period. Site personnel should make every effort to initiate study drug treatment within three days after randomization.

On-Treatment Period: The on-treatment period has three phases: the first two cycles, cycles 3-18, and cycle 19 and beyond. All cycles are 28 days in duration. The first two cycles are characterized by weekly visits, safety assessments, and, in the experimental arm, elotuzumab infusions. Cycles 3-18 are characterized by fortnightly visits, safety assessments and, in the experimental arm, elotuzumab infusions. Cycles 19 and beyond, are characterized by once every 4 weeks visit, safety assessments and, in the experimental arm, elotuzumab infusions. Subjects should have myeloma urine and serum laboratory assessments every four weeks while on treatment until they progress and should have imaging for extramedullary plasmacytomas, if indicated, and at the time of CR/sCR assessment. The timing of the tumor assessments will be independent of dosing. Study treatment ends when the subject progresses, experiences unacceptable toxicity, or withdraws consent.

Follow-up Period: Subjects who discontinue study therapy prior to progression must continue to undergo tumor assessments on the same schedule used in the on-treatment period, regardless of whether they are receiving new anti-myeloma therapy. The only exception to this is if the subject withdraws consent for all study procedures or loses the ability to consent freely.

Follow-up for survival and subsequent myeloma therapy will be conducted every 16 weeks until the subject dies or the study ends.

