7.5 Efficacy

Efficacy analyses (PFS, ORR and OS) will be conducted on the population of all randomized subjects, grouped by arm assigned at randomization, unless otherwise noted.

The main analyses of PFS and ORR will be based on IRC evaluation. Unless stated otherwise, whenever a stratified analysis is specified, the stratifications factors will be those used in the randomization (per IVRS), that is:

- Stage of disease (ISS 1 – 2 versus 3)
- Age (< 75 years old versus \geq 75 years old)
- ECOG Performance status (0 versus 1 - 2)

All p-values reported will be two-sided. Confidence intervals (CI) for the PFS and OS endpoints will be based on the nominal significance level adjusted for the interim analyses to preserve the overall type I error rate. Two-sided 95% CI will also be provided. CIs for the other endpoints will be at the two-sided 95% level. The p-values presented in the clinical study report will be rounded to the fourth decimal place. Point estimates and confidence bounds for efficacy variables will be rounded to the second decimal place.

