7.5.9 Analyses of Overall Survival

Overall survival will be compared between the treatment arms at the interim and final analyses, using a two-sided stratified log-rank test. The stratification factors will be those used in the analysis of PFS.

An O'Brien and Fleming α -spending function will be employed to determine the nominal significance levels for the interim and final analyses.

All analyses performed for PFS (detailed in [section 7.5.1](#)) will be repeated for OS. Supportive analyses 1, 2, 4 and 5 of PFS (detailed in [section 7.5.2](#)) as well as the subset analyses (detailed in [section 7.5.4](#)) will also be repeated for OS. These will be conducted only at the time of the final analysis of OS.

Estimates for 1, 2, 3, 4, and 5-year OS rates will be presented along with their associated 95% CIs when appropriate follow-up time has occurred. These estimates will come from the KM curve and their standard errors (SEs) used in constructing CIs, will be computed using Greenwood's formula¹⁷ and the log-log transformation applied on the survivor function.

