7.5.11 Hierarchy for Testing Secondary Endpoints

A hierarchical procedure will be used to preserve a two-sided family-wise type I error rate of 5% for testing one primary (PFS) and two key secondary endpoints (ORR and OS) in this study.

If there is a statistically significant improvement in PFS, ORR will be compared between treatment arms at the two-sided 5% alpha level. If, and only if, the comparison of ORR is statistically significant, then OS will be compared between treatment arms using a 5% sequential test procedure.

The two QOL secondary endpoints will not be part of the hierarchical testing and will be tested independently of the significance of the other endpoints. Each of the two comparisons will be made at the two-sided type I error of 2.5%.

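### The BPI-SF pain model in the Protocol leaves out the three randomization factors, which may cost the two pain tests a little power

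*Protocol*

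**What the plan says.** The synopsis gives the model for both BPI-SF endpoints as a "longitudinal mixed model with treatment arm and time point (categorical) and baseline score as fixed effects and a banded covariance matrix". Protocol 8.4.7.1 gives the same model for pain severity, a "longitudinal mixed model with treatment arm, time point (categorical), and baseline score as fixed effects and a banded covariance matrix", and a similar one for pain interference. ISS stage, age group and ECOG status appear in neither place.

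Both endpoints are formally tested outside the hierarchy. SAP 7.5.11 states: "Each of the two comparisons will be made at the two-sided type I error of 2.5" percent. Protocol 8.4.2.3 agrees.

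The three factors are used elsewhere:
- **Randomization (Protocol 4.2):** stratified by ISS 1-2 vs 3, age under 75 vs 75 and over, and ECOG 0 vs 1-2, "and will be carried out via permuted blocks within each stratum".
- **PFS (Protocol 8.4.2.1, SAP 7.5.1):** stratified log-rank test.
- **ORR (Protocol 8.4.2.3):** a CMH "test stratified by the same factors used in the analysis of PFS".
- **OS (SAP 7.5.9):** "The stratification factors will be those used in the analysis of PFS".

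SAP 7.5 has a general rule: "Unless stated otherwise, whenever a stratified analysis is specified, the stratifications factors will be those used in the randomization (per IVRS"). The visible SAP text gives no model for the BPI-SF.

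**The concern.** Every other formally tested endpoint is analysed with the randomization factors; the two pain endpoints are not, and no reason is given. The SAP's general rule does not close the gap. It applies only where a stratified analysis has been specified, and the pain model has not been specified as one.

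Permuted blocks within strata balance the arms on the three factors, so differences between strata add almost nothing to the true sampling variance of the treatment comparison. A model that omits the factors leaves those differences in its residual variance. Its reported standard error is then larger than the true one, its confidence intervals are too wide, and its test rejects too rarely. What is at stake is power for the two pain comparisons. PFS, ORR and OS are untouched.

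A smaller point concerns the baseline score, which is a covariate in this model. SAP 6.1 says: "For analyses purposes data collected within 60 days of randomization and prior to first dose will fall into the screening/baseline period". SAP 8.1 requires baseline evaluations to precede the first dosing date, and its exception for same-day assessments names laboratory tests and procedures but not questionnaires. The two sections therefore differ on whether a BPI-SF completed before dosing on Cycle 1 Day 1 can be the baseline. Table 5.1-1 also schedules a BPI-SF at screening, so a baseline score should exist under either reading.

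**Working it through.** **Inputs.** From the documents: two-sided 2.5% per endpoint (0.025 + 0.025 = 0.05 for the pair), 1:1 allocation, about 750 subjects, and 2 × 2 × 2 = 8 strata. The documents state no power, effect size, SD or variance share for the BPI-SF, so there is no planned figure to reproduce. The 80% reference power and every R² below are assumptions. R² is the share of variance remaining after the baseline score that the three factors explain.

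**Closed form: R² as a share of the variance of a subject's average change.** The critical value is z = 2.2414. Under stratified randomization the model without the factors reports a standard error too large by k = 1/√(1 − R²). Hence:
- true size = 2 × [1 − Φ(z·k)]
- CI width ratio = k
- power, where the model with the factors has 80% = Φ(z + 0.8416 − z·k)

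At R² = 5%, k = 1/√0.95 = 1.026 and z·k = 2.2996. Size is 2 × [1 − Φ(2.2996)] = 0.0215, and power is Φ(3.0830 − 2.2996) = Φ(0.7834) = 78.3%.

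| Assumed R² | True size (nominal 0.025) | CI ratio | Power without factors |
|---|---|---|---|
| 0% | 0.0250 | 1.000 | 80.0% |
| 2% | 0.0236 | 1.010 | 79.4% |
| 5% | 0.0215 | 1.026 | 78.3% |
| 10% | 0.0181 | 1.054 | 76.4% |

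A simulated ANCOVA of a subject-level mean (750 subjects, permuted blocks of 4 in 8 strata) agrees. At R² = 10%, power was 76.4% without the factors and 79.9% with them; size was 0.0179 and 0.0234.

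**Repeated measures: R² as a share of the variance at a single visit.** Averaging over visits shrinks visit-level noise but not a stratum effect that is constant over time, so the same R² has more weight. The effective share is R² × E[s²]/E[s], where s = 1′V⁻¹1 and V is the covariance of a subject's observed visits with the stratum effect included.

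Example: all 24 visits observed, within-stratum correlation 0.5, R² = 10%. The correlation including strata is 0.9 × 0.5 + 0.1 = 0.55. Then s = 24/(1 + 23 × 0.55) = 24/13.65 = 1.758, and the effective share is 17.6%. Across three correlation structures and dropout medians of 12, 25 and 33.75 months, assumed R² of 2%, 5% and 10% become 3.5-4.0%, 8.5-9.7% and 16.4-18.4%.

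A simulation of the repeated-measures model with banded covariance assumed 700 subjects, 24 four-weekly visits, unequal strata (factor prevalences 0.40, 0.30 and 0.35), and exponential dropout with the PFS medians of Protocol 8.1 (25 and 33.75 months). There were 20,000 runs per cell. The ranges cover the three correlation structures.

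| Assumed R² | Power without factors | CI ratio, without/with | Size without factors |
|---|---|---|---|
| 0% | 79.2-79.7% | 1.002 | 0.0266-0.0285 |
| 2% | 78.0-78.7% | 1.021-1.023 | 0.0222-0.0238 |
| 5% | 76.5-76.8% | 1.050-1.054 | 0.0174-0.0192 |
| 10% | 72.1-73.4% | 1.101-1.109 | 0.0137-0.0154 |

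With the factors, power was 79.4-80.4% throughout. At R² = 0, size with the factors was 0.0268-0.0286, so adding them cost nothing detectable.

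Cross-check: putting the mid-range CI ratio at R² = 10%, 1.105, into the closed form gives Φ(3.0830 − 2.2414 × 1.105) = 72.8%, inside the simulated range. A separate repeated-measures simulation, with known covariance and one correlation structure, gave power without and with the factors of 76.6% and 80.1% at R² = 5%, and 72.2% and 79.1% at 10%.

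**The case against.** **The gap may already be closed.** The SAP commits to analysing subject-reported outcomes (6.3), but that section is not visible, and there is redacted text after the model paragraph in Protocol 8.4.7.1. This stands as a limit: no gap in the SAP is shown. The Protocol's own list of fixed effects is legible, however, and is the same in both places. If the SAP does add the factors, the Protocol needs aligning.

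**No error is shown.** The treatment estimate is unbiased, type I error is not inflated and no stated power is undermined. All true. This is a question of efficiency.

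**The loss rests on assumed R² values, and the baseline score is already in the model.** Also true. The documents do not show that the factors predict pain change. A link is plausible, because ECOG status (Appendix 2) is graded on symptoms and mobility and the BPI-SF interference items (Appendix 5) include walking, activity and work, but it is not established.

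**The repeated-measures simulation rests on many inputs outside the documents, and its size with the factors varies more than expected.** It was 0.0268-0.0286 at R² = 0 but 0.0228-0.0253 at 5%, with a Monte Carlo standard error of about 0.0011. The values above 0.025 at R² = 0 occur with and without the factors and probably reflect the moment estimator and normal reference. The simulation should be read for direction and rough size. Its power figures are supported by the closed-form cross-check and the separate simulation.

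**The baseline-definition point is a separate matter with no demonstrated effect.** Fair; it is kept only as a minor wording item.

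**Conclusion.** The concern holds for the Protocol as written. Both statements of the BPI-SF model omit the three randomization factors, and no visible rule brings them in. The consequence is a possible loss of power, not invalid inference.

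From an assumed 80%, the closed-form loss is 0, 0.6, 1.7 or 3.6 percentage points at R² of 0%, 2%, 5% or 10% of the variance of a subject's average change. If the same shares apply to single visits and the stratum effect is constant over time, the loss at 10% is about 7 to 8 points (power 72-73%). All of this depends on R², which the documents do not give, and on the unseen SAP section not already including the factors. The change is worth making because it costs almost nothing.

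**What to change.** Add ISS stage (1-2 vs 3), age group (under 75 vs 75 and over) and ECOG status (0 vs 1-2), as recorded in the IVRS, as fixed effects in the pain severity and pain interference models. Change the synopsis and Protocol 8.4.7.1, and the SAP unless its redacted section already does this. If the factors are left out on purpose, state why. Settle this before unblinding so that covariates are not chosen from the data.

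Minor: reconcile SAP 6.1 with 8.1 by adding questionnaires completed before dosing on the first dosing date to the same-day exception, unless the redacted text already covers it.

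The cost is a few words and three model terms per endpoint. The factors are already collected.

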8.4.8 Other Analyses

[REDACTED]

PFS rates at 1, 2, 3, 4, and 5 years will be estimated from the KM curve. Each analysis will be performed after all subjects have been followed for the appropriate time. [REDACTED]

[REDACTED]

[REDACTED]

[REDACTED]

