Survival, a key secondary endpoint, will be compared at an interim analysis between the two arms at the time of the interim analysis of PFS provided that PFS and ORR analyses are positive. The final survival analysis will take place after 354 deaths, which is projected to occur 7 years (84 months) after the initiation of the study. An O'Brien and Fleming α -spending function will be used to obtain the nominal significance levels for the interim and final analyses of survival. Three hundred and fifty-four (354) deaths ensure that a two-sided 5% level sequential test procedure with one interim analysis will have 80% power for a 8.7 percentage point improvement in 4-year survival rate from 59.0% to 67.7%, ie, for a HR = 0.74.

Power calculations were done using East v5.1 software. (See [Section 8.1](#), Sample Size Determination, for more detail.)

Endpoint Definitions and Analyses

The primary endpoint in this study is progression-free survival (PFS), which is defined as the time from randomization to the date of the first documented tumor progression, as determined by the IRC using EBMT criteria,

or to death. Subjects who neither progress nor die will be censored on the date of their last disease assessment, provided death does not occur more than 10 weeks after the last tumor assessment.

The following censoring rules will be applied to PFS:

- Subjects who receive systemic secondary anti-myeloma therapy prior to documented progression will be censored on the date of their last tumor assessment prior to initiation of new therapy
- Subjects who have an event > 10 weeks after the last prior tumor assessment will be censored at the last prior assessment
- Subjects who do not progress and who do not receive subsequent therapy will be censored at their last tumor assessment

See [Section 8.3](#), Endpoint Definitions, for more detail on the definition of PFS.

A stratified log-rank test will be used to compare PFS between treatment arms. The factors will be the same as those used in the randomization. The hazard ratio of the experimental to the control arm and corresponding two-sided 95% confidence interval will be calculated using a stratified Cox proportional hazards model with treatment as the sole covariate. The Kaplan-Meier product limit method will be used to display PFS curves and PFS rates at 1-5 years will be obtained from those curves. Each rate will be estimated after all subjects have been followed for the appropriate time.

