1.3.2 Secondary Objectives

- To compare objective response rate between treatment arms
- To compare overall survival between treatment arms
- To compare the change from baseline of the mean score of pain severity and the change from baseline of the mean score of pain interference using the Brief Pain Inventory- Short Form (BPI-SF) between treatment arms
- To assess PFS rates at 1, 2, 3, 4, and 5 years.

[REDACTED]

[REDACTED]

[Redacted text block]

[Redacted text block]

[Redacted text block]

[Redacted text block]

[Redacted text block]

[REDACTED]

[REDACTED]

[REDACTED]

[REDACTED]

[REDACTED]

[REDACTED]

[REDACTED]

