Tumor assessments, based on the EBMT criteria, will be conducted every 4 weeks (-1/+3 days) relative to the first dose of study medication until disease progression, death or withdrawal of consent. The date of progression, best response and date of response used in the primary efficacy analyses will be based on the independent review committee (IRC) assessments as well as the investigators. All subjects must continue to have protocol-specified tumor assessments until disease progression (even if the subject is off study therapy or has started on a new anti-myeloma therapy, as specified in the ITT definition of PFS in [Section 8.3.1](#)), death, or withdrawal of consent from the study. Once subjects reach disease progression, they shall be followed at least every 16 weeks after disease progression for overall survival and subsequent myeloma therapy. Cross-over between the arms is not permitted.

An independent DMC will conduct regular safety reviews throughout this trial. In addition, there will be a pre-planned interim analysis for safety and PFS once the following two conditions have been met: at least 338 (70%) progression events have been observed per IRC and all subjects have been randomized.

Subjects who receive any non-protocol specified systemic anti-myeloma therapy prior to documented progression will be discontinued from study treatment (see [Section 3.5](#)). However, tumor assessments should continue at 4 week intervals until documented progression to comply with the intent to treat analysis ([Section 8.3.1](#)).

Subjects will continue to be followed until the last subject has the last follow-up visit which is projected to occur approximately 7 years from the first randomized subject.

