8 STATISTICAL CONSIDERATIONS

8.1 Sample Size Determination

The number of events and power for PFS were calculated assuming an exponential distribution in each arm. One interim analysis of PFS is planned. The comparisons of PFS will be carried out using log-rank tests stratified by stage of disease (International Staging System 1 - 2 versus 3), ECOG performance status (0 versus 1 - 2), and age (< 75 years old versus \geq 75 years old). The interim analysis will allow for early stopping for superiority. An O'Brien and Fleming α spending function will be employed to determine the stopping boundaries.

Approximately 750 subjects will be randomized to the 2 treatment groups in a 1 to 1 ratio in order to obtain at least 482 progression events, ie, documented progressions or deaths as determined by the IRC. Four hundred and eighty-two (482) events ensure that a two-sided, 5% level, sequential test procedure with 1 interim analysis after 70% of the total events (338) will have 90.5% power if the median PFS times in the control and experimental arms are 25 and 33.75 months, respectively, ie, if the hazard ratio of the experimental to control arm is 0.74. Assuming an accrual rate of 24 subjects per month, it will take approximately 60 months to obtain the required number of events, 31 months for accrual and 29 months for PFS follow-up. It is projected that at the time of final PFS analysis (at least 482 events), an observed hazard ratio of 0.84 or less, which corresponds to a 4.8 month or greater improvement in median PFS (25 vs 29.8 months), would result in a statistically significant improvement in PFS for the elotuzumab-containing arm. In view of evolving results with frontline lenalidomide therapy, a reassessment of the sample size could be made. The decision to reevaluate sample size would be based on external data only and would not involve a change in the required number of PFS events.

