Survival, a key secondary endpoint, will be compared between the two arms at the time of the interim analysis of PFS (if and only if both PFS and ORR are positive), and again after 354 deaths, which is projected to occur 7 years (84 months) after the initiation of the study. An O'Brien and Fleming α -spending function will be used to obtain the nominal significance levels for the interim and final analyses of survival. Three hundred and fifty-four (354) deaths ensure that a two-sided 5% level sequential test procedure with one interim analysis will have 80% power for a 8.7 percentage point improvement in 4-year survival rate from 59.0%³⁶ to 67.7%, ie, for a HR = 0.74.

Power calculations were done using East v5.1.

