8.5 Interim Analyses

A data monitoring committee (DMC) will be established before the first subject is treated and will monitor safety throughout the study. (The DMC will receive SAE tables every 4 months and more comprehensive safety data every 8 months.) In addition, the DMC will review safety and efficacy data once the following two conditions have been met: at least 338 progression events have been observed and all subjects have been randomized.

A key feature of the interim analysis after at least 338 (70%) progression events will be a formal comparison of PFS between treatment arms. This formal comparison of PFS will allow for early stopping for superiority. The stopping boundaries will be derived based on the O'Brien and Fleming α spending function in East v5.1. (Under current accrual assumptions, the 338 progression event milestone will occur approximately 41 months after study start.)

The stopping boundaries for superiority will depend on the actual number of events observed at the time of the interim analysis, and will be determined using the interim monitoring tool in East v5.1. However, if there were exactly 338 events the DMC could stop the study for superiority if the p-value were ≤ 0.0148 . (It should be noted that survival follow-up would continue even if the study were stopped at the interim analysis of PFS for superiority.)

A formal interim analysis of OS will be conducted provided that both the analyses of PFS and ORR are positive (refer to [Section 8.4.2.3](#) for further detail). The final analysis of survival, provided that the survival portion of the study is not stopped early, will take place after at least 354 deaths have been observed, which is projected to occur approximately 7 years after the first subject is randomized. The nominal significance levels for the interim and final survival comparisons will be determined by an O'Brien and Fleming alpha spending function.

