4 ENDPOINTS

The primary endpoint is PFS based on IRC tumor assessments using the primary definition of PFS (see [section 4.1.1.3](#)). Supportive analyses of PFS are:

- [REDACTED]
- [REDACTED]
- [REDACTED]

The secondary endpoints are:

- ORR. The primary analysis will be based on IRC tumor assessments using the EBMT assessment criteria. Supportive analysis of ORR will be based on investigator assessment of best response.
- OS
- Patient-reported Outcomes (BPI-SF)
- PFS rates at 1, 2, 3, 4, and 5 years

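### Does the follow-up condition on the landmark PFS rates leave the 5-year rate without a date at which it can be estimated?

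*Protocol*

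**What the plan says.** Protocol 1.3.2 lists as a secondary objective "To assess PFS rates at 1, 2, 3, 4, and 5 years", and SAP section 4 lists the same rates as a secondary endpoint. Protocol 8.4.8 takes them from the Kaplan-Meier curve and adds "Each analysis will be performed after all subjects have been followed for the appropriate time". The synopsis says the same: "Each rate will be estimated after all subjects have been followed for the appropriate time". Neither place defines the appropriate time. Text beside the sentence in 8.4.8 is redacted.

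On timing, Protocol 8.1 assumes 24 subjects per month and states that "it will take approximately 60 months to obtain the required number of events, 31 months for accrual and 29 months for PFS follow-up". Protocol 3.1 says "Subjects will continue to be followed until the last subject has the last follow-up visit which is projected to occur approximately 7 years", counted from the first randomized subject. Protocol 8.1 has survival compared at the PFS interim analysis and "again after 354 deaths, which is projected to occur 7 years (84 months) after the initiation of the study". Protocol 8.5 places the final survival analysis "after at least 354 deaths have been observed, which is projected to occur approximately 7 years after the first subject is randomized".

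SAP 7.5.1 presents the 1- to 5-year PFS rates where that is appropriate, with Greenwood standard errors and log-log 95% confidence intervals. SAP 7.5.9 treats the survival rates in the same way and ties them explicitly to sufficient follow-up having accrued.

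**The concern.** The condition and the timeline seem to conflict. If the last subject enters at about month 31, nobody can say before about month 91 that every subject has had five years in the study, yet follow-up is projected to end at about month 84. Taken at its word, the protocol would then list a secondary endpoint that has no permitted estimation date within the trial.

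No readable sentence says whether the 5-year rate would then be dropped, postponed or estimated with incomplete follow-up. Someone would have to choose late in the study, when PFS results may already be known. At stake is one reported secondary estimate and the appearance of a choice made after the fact.

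**Working it through.** **Inputs.** From Protocol 8.1: 750 subjects, 1:1, 24 per month; exponential PFS with medians 25 and 33.75 months; 4-year survival 59.0% and 67.7%. The documents state no dropout rate, so zero is used first.

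**The plan's own dates.** Accrual lasts R = 750/24 = 31.25 months (plan: 31). With uniform entry, expected events per arm at month T (after accrual ends) are (375/R) × ∫₀ᴿ [1 − exp(−λ(T − x))] dx. Use λ = ln 2/median for PFS and λ = −ln(4-year survival)/48 for OS, sum over the arms, and solve for T.

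| Milestone | Computed month | Plan |
|---|---|---|
| 338 PFS events | 41.6 | about 41 |
| 482 PFS events | 59.7 | about 60 |
| 354 deaths | 83.3 | 84 |

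The timeline reproduces.

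**When the condition is met.** Read the follow-up as time since randomization, the lenient reading. The k-year condition is then met at 31.25 + 12k.

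| Rate | Month met | Against month 84 |
|---|---|---|
| 1-year | 43.25 | met |
| 2-year | 55.25 | met |
| 3-year | 67.25 | met |
| 4-year | 79.25 | met, 4.75 months to spare |
| 5-year | 91.25 | 7.25 months late |

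At month 84 the last entrant has 84 − 31.25 = 52.75 months. Those who entered by month 24 number 24 × 24 = 576 and have at least 60 months; the other 174 (23%) do not.

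**How firm month 84 is.** It is the projected date of 354 deaths with nobody lost. Adding an assumed constant loss to survival follow-up moves it:

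| Assumed loss per month | Month of 354 deaths |
|---|---|
| 0 | 83.3 |
| 0.1% | 86.4 |
| 0.2% | 89.9 |
| 0.3% | 93.9 |

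It reaches 91.25 at 0.236% per month (12 × 0.236 = 2.8% a year), or with no loss if death hazards are 0.894 of plan, about 11% lower.

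**What estimating at month 84 costs.** True 5-year PFS under the plan is 0.5^(60/25) = 0.1895 for Ld and 0.5^(60/33.75) = 0.2916 for E-Ld. Let G(u) be the share of subjects with potential follow-up beyond u months; at month 84, G(60) = 24/31.25 = 0.768. Expected numbers at risk at 60 months are 375 × S(60) × G(60). The large-sample Greenwood variance is (S(60)²/375) × ∫₀⁶⁰ λ/[S(u)G(u)] du. At month 91.25, G = 1 up to 60 months and this reduces to S(1 − S)/375; for Ld, √(0.1895 × 0.8105/375) = 0.0202.

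| Cut (month) | At risk, Ld / E-Ld | SE in points, Ld / E-Ld | Log-log 95% CI width in points |
|---|---|---|---|
| 80 | 45 / 70 | 2.11 / 2.43 | 8.2 / 9.5 |
| 84 | 55 / 84 | 2.06 / 2.38 | 8.0 / 9.3 |
| 91.25 | 71 / 109 | 2.02 / 2.35 | 7.9 / 9.2 |

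Moving from month 91.25 to month 84 adds less than 0.1 point to either standard error. All three rows ignore the primary definition's censoring at new therapy and after long assessment gaps (Protocol 8.3.1, SAP 4.1.1.3). Real numbers at risk will be lower at every cut, so the absolute precision is a best case.

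**The case for a change.** The strongest case for a change is that the arithmetic is the plan's own, the condition appears twice in the protocol, and the SAP's conditional wording is undefined. The parallel wording for survival suggests that it restates the follow-up condition and supplies no fallback. One sentence would settle the matter with no extra visits or subjects. The timing can also move the other way: Protocol 8.5 allows the survival part to stop early, which would widen the gap.

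The arithmetic and the missing definition stand. Three parts are weaker.

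- **A data-driven choice.** Whether all subjects have 60 months depends on the last randomization date and the data cut. The first is known once accrual ends, which must precede the PFS interim analysis. The second is set by a pooled count of deaths. Results by arm enter neither, so the shortfall can be foreseen years ahead. SAP 7.5.1 also displays the PFS curve for each arm, which limits what selective reporting of one point on it could achieve.
- **No handling at all.** Read together, SAP 7.5.1 and 7.5.9 present a landmark if follow-up supports it and otherwise do not. That is terse, but it is a rule. The redacted text in 8.4.8 may say more and cannot be counted as absent.
- **A cost-free remedy.** Tying the 5-year rate to the final survival cut presumes IRC-assessed PFS up to that date. The final PFS analysis is projected at about month 60, and no readable section schedules IRC review as late as month 84.

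**Conclusion.** No change is needed. On the projections, the all-subjects condition for the 5-year PFS rate falls about 7 months after the expected end of follow-up; the 1- to 4-year rates are unaffected. The shortfall is measured against an approximate, event-driven date and lies within ordinary planning error for an 84-month horizon.

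What is missing is a definition that an analyst would supply without difficulty: report the 5-year Kaplan-Meier estimate with its planned interval if follow-up supports it, and otherwise leave it out, as the SAP's conditional wording permits. Under the plan's assumptions the choice of cut changes the standard error by less than 0.1 percentage point. The rates are untested and lie outside the hierarchy in SAP 7.5.11, so type I error, power and every formal conclusion stay the same.

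This rests on uniform accrual at 24 per month, exponential PFS and survival as planned, follow-up read as time since randomization, and precision computed without the primary definition's extra censoring.
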